4. SUBJECT SELECTION

4.0 Subject Recruitment

Participants will be recruited from the UM and UW MS Clinics tertiary clinics. Additional participants will be recruited through UM and UW medical records; other neurology practices throughout Mid- and Southeastern Michigan (by invitation) and the Pacific Northwest, UM and UW electronic clinical trials registries; advertisement through community outlets (e.g., posting flyers in community centers, distributing flyers and fund raising walks), clinicaltrials.gov; Facebook and other social media campaigns, iConquerMS, and from advertisements posted by the NMSS (study stakeholder).

The table below shows the current enrollment plan for data collection.

Total number of study participants expected to be screened:	360
Of those screened, total number of study participants expected to be eligible:	340
Of those eligible, total number of study participants enrolled:	330
Target sample size (i.e., of those eligible, total number of study participants expected to be enrolled):	300 completers

We anticipate enrolling 50 subjects per site in year 1, 65 subjects per site in year 2, and 50 per site subjects in year 3, or an average of 4-5 subjects per month per site throughout the course of the study.

4.1 Inclusion Criteria

1. Patients with clinically definite MS (all MS subtypes included, regardless of disease duration, disability level, or disease modifying therapy status);

2. Age 18 years or older;
3. Presence of chronic, problematic fatigue that, in the opinion of the patient, has interfered with their daily activities for ≥ 3 months;
4. Average Fatigue Severity Scale (FSS) score greater or equal to 4 at screening.
5. Access to the internet with video-capable smart phone or computer if performing study remotely (virtual visit).

4.2 Exclusion Criteria

1. Current shift work sleep disorder, or narcolepsy diagnosed with polysomnography and multiple sleep latency test (diagnoses in which modafinil is already widely accepted as symptomatic care)
2. History of MS relapse within the last 30 days prior to screening (participants will be considered eligible after the 30-day window);
3. Current stimulant or wake-promoting agent use such as amantadine (Symmetrel), modafinil (Provigil), short or long acting methylphenidate (Ritalin/Concerta), dextroamphetamine (Dexedrine), dextroamphetamine-amphetamine (Adderall, Adderall XR), lisodexamfetamine (Vyvanse), armodafinil (Nuvigil), or amphetamine (Adzenys XR-ODT, Dyanavel XR, and Evekeo) within 30 days of screening (if present, patients could still be eligible after a 30-day washout);
4. For female participants only: Pregnancy or breastfeeding (modafinil is contraindicated in these conditions);
5. For female participants only: Reliance on hormonal contraception (such as birth control pills, shots, implants, patches, vaginal rings) AND concomitant unwillingness to use alternative non-hormonal means of birth control (spermicide or condoms) during the course of the study (modafinil can decrease the effectiveness of oral contraception);
6. Current suicidal ideation (SI) with intent or plan (per a response of ≥ 1 on the suicide item from the Patient Health Questionnaire-9); these individuals will be assessed by a study psychologist and referred for urgent mental health treatment† (people with SI but no intent or plan will be included).
7. Known hypersensitivity to modafinil or armodafinil or its inactive ingredients.
8. History of the following cardiovascular conditions: recent myocardial infarction (last 6 months prior to screening), unstable angina, left ventricular hypertrophy, mitral valve prolapse, NYHA class III or IV congestive heart failure
9. Diagnosis of hypertension within the past year not managed by a health care provider
10. Recent history (within 1 year) of prescription or illicit stimulant abuse (such as cocaine, amphetamine, methamphetamine)
11. Any other medical, neurological, or psychiatric condition that, in the opinion of the investigators, could affect participant safety or eligibility.

†Participant behavior or comments that suggest imminent threat will prompt immediate 911 activation. Behavior or comments that suggest SI with plan but no immediate threat will prompt psychiatric ER referral

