Modafinil: Use of modafinil involves a minor increase over minimal risk. Modafinil is generally considered to be safe and well tolerated. The most common adverse reactions (5%) associated with modafinil which occurred more frequently than placebo-treated patients in previous clinical trials were headache, nausea, nervousness, rhinitis, diarrhea, back pain, anxiety, insomnia, dizziness, and dyspepsia. It is recommended that caution be used in patients with a history of psychosis, depression, or mania, to avoid exacerbation of these conditions. Serious rash requiring hospitalization and discontinuation of treatment has rarely been reported. Life-threatening skin conditions such as Steven-Johnson Syndrome or Toxic Epidermal Necrosis Syndrome, angioedema, anaphylaxis, hypersensitivity reactions involving multiple organs, new or increased psychiatric symptoms (including worsening depression, mania, depression, suicidality), or increased blood pressure are possible. Dose reduction is recommended in patients with severe hepatic impairment. Modafinil use may decrease the effectiveness of hormonal contraception, use of alternative or concomitant methods of contraception while taking modafinil and for one month after discontinuation of modafinil treatment is recommended. Elimination of drugs that are substrates for CYP2C19 (e.g., phenytoin, diazepam, propranolol, omeprazole, and clomipramine) may be prolonged by modafinil via inhibition of metabolic enzymes, with resultant higher systemic exposure.

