All potential risks of modafinil will be outlined in the informed consent document and discussed with the patient prior to enrollment. Patients will also be advised that there may be unforeseen risks not outlined in the ICF. Based on the package insert, eligibility criteria will exclude pregnant women, and a urine pregnancy test will be required prior to study enrollment. Women of childbearing age will be advised of the risk of decreased effectiveness of hormonal contraception with modafinil use and be advised to use a form of birth control that does not involve hormonal contraception (spermicide or condoms) during the study and for one month after discontinuation of modafinil treatment. Participants with a history of hepatic impairment, participants over age 65, and participants who use warfarin, phenytoin, MAOIs and cyclosporine will be given dose limitations that will not exceed half of the maximal daily dose for healthy patients (50-100 mg once-twice daily as tolerated). Patients will be advised to monitor for common side effects of modafinil including headache, nausea, nervousness, rhinitis, diarrhea, back pain, anxiety, insomnia, dizziness, and dyspepsia while on modafinil, and if these symptoms occur or worsen, to alert the study team, during which time dose reduction or discontinuation will be discussed. Participants who experience worsening depressive symptoms, psychosis, increased suicidality, or suspected allergic reactions (rash, hives, mouth sores, blisters, swelling of the face, eyes, lips, tongue, or throat, trouble swallowing or breathing, fever, shortness of breath, swelling of the legs, yellowing of the skin or whites of the eyes, or dark urine) will be instructed to stop treatment immediately and contact the study team. Participants are also advised not to consume alcohol per the drug label. Participants should be instructed to call study team when new drugs are added or removed from their drug regimens so that drug interactions can be assessed. Participants may choose to discontinue their treatment at any time if they experience any untoward effects that they believe are related to modafinil, but will be encouraged to remain in the study until completion for monitoring. Adverse events and severe adverse events will be assessed/reported regularly and on an as-needed basis in accordance with the protocol, GCP, and IRB standards (see sections 7.5 and 8). Action involving possible PI discontinuation of study drug will be determined promptly in accordance with the protocol, GCP and IRB guidelines, as well as the medical monitor (see section 10 and 13).

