Working with thoughts (part 2) - Challenging unhelpful thoughts, evidence gathering, alternative thoughts; relaxation practice; energy management check-in
Managing emotions - Emotions and fatigue, living in the present, nurturing positive emotions, gratitude, guided imagery; energy management check-in
Building resilience and moving forward - Designing a personal fatigue self-management plan, skills relapse prevention, building resilience
Two 15-20 minute calls between weeks 8-12, to review and troubleshoot implementation of fatigue self-management skills, including their personal self-management plan.

Modafinil: Modafinil will be prescribed by one of the neurologists on the study team. Modafinil (2-[(diphenylmethyl) sulfinyl]acetamide) is a centrally-acting oral agent that is FDA-approved to improve wakefulness in patients with excessive sleepiness associated with narcolepsy, obstructive sleep apnea, or shift work disorder. The mechanism(s) through which modafinil promotes wakefulness is unknown. Modafinil's benefits for fatigue in MS have been demonstrated in 5 previous studies. Three successful open label studies that used various subjective fatigue measures, demonstrated a benefit of modafinil on fatigue intensity. A single-blind placebo-controlled study also demonstrated a significant improvement in fatigue intensity with modafinil in a recent study. One 8-week double-blind placebo-controlled trial which examined the effects of modafinil on fatigue intensity showed a significant improvement in fatigue with modafinil.

Modafinil will be dispensed for Group 2 and 3 patients following 1 week of baseline actigraphy monitoring and at 8 weeks. At baseline, participants will be prescribed the 100 mg pills (enough to take up to 4 pills per day). They will be advised to take 100 mg once a day (upon awakening) as a starting point for the first week. Depending on results, participants will be allowed to adjust their dose based on the following scenarios:

- If the 100 mg/day dose effectively treats their fatigue throughout the day, participants will remain on this dose.
- If the 100 mg/day dose is adequate, but of insufficient duration, participants will be allowed to take another half pill or full pill around lunchtime (early afternoon: at least 8 hours before bedtime) for a total dose of 150 mg or 200 mg a day.

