6.1 Screening/Baseline Visit

Depending on state or institutional COVID-19 restrictions at time of screening, baseline visits may be conducted virtually (via video meeting) or in-person. Even when in-person visits are permitted, participants will still be given the option for virtual visits.

For in-person visits, subjects will be seen at one of several UM or UW sites for baseline visit activities, including but not limited to the University of Michigan Taubman Neurology Clinic, Michigan Clinical Research Unit (MCRU), and the UW Medicine Multiple Sclerosis Center.

Informed consent will be obtained by qualified study staff. Inclusion and Exclusion Criteria will be reviewed. For virtual visits, the informed consent will be obtained digitally. See section 7.2.4.

The screening portion of this visit will include confirmation of eligibility via:

- 1) Participant self-report (e.g. FSS, PHQ-3, etc.)
- 2) Demographic information
- 3) Focused medical and surgical history as it relates to multiple sclerosis (subtype, prior disease modifying therapy use, disease duration), fatigue, mood disorders and hepatic issues (for modafinil)
- 4) Medication review

5) Neurologist assessment of eligibility

6) Pregnancy test (For individuals of childbearing age who identify their pregnancy status as unsure)

Eligible subjects will be randomized into one of the 3 study arms & will complete baseline assessments of self-reported fatigue, disability, sleep, exercise, self-efficacy, and other quality of life factors via online Redcap surveys.

6.2 Home monitoring 7-day PRO-Diary application (EMA) – BASELINE AND WEEK 12 ONLY: After completing the above screening/baseline activities, participants will receive instruction on use of the PRO-Diary® accelerometer watch, which the participant will wear during two separate 7-day “home monitoring” periods, at baseline (sent home with watch following baseline visit) and 12 weeks to assess physical activity (objectively measured via accelerometry), AND ecological momentary assessment (EMA) of fatigue intensity, fatigue impact, fatigability (ration of fatigue intensity/accelerometer activity counts), and sleep. See “Assessments” section.

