12.2 Subject Information and Consent

A study team member will explain to each subject the nature of the study, its purpose, the procedures involved, the expected duration, the potential risks and benefits involved and any discomfort it may entail. Each subject will be informed that participation in the study is voluntary and that he/she may withdraw from the study at any time and that withdrawal of consent will not affect his/her subsequent medical treatment or relationship with the treating physician.

This informed consent will be given by means of a standard written statement, written in non-technical language. The subject should read and consider the statement before signing and dating it, and should be given a copy of the signed document. No patient can enter the study before his/her informed consent has been obtained.

The informed consent form is considered to be part of the protocol, and will be submitted for IRB approval.

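### Section 4.2 item 5 makes non-hormonal contraception an entry condition only for women on hormonal methods, so a woman who uses none and will use none still qualifies; separately, sections 1.3 and 6.1 disagree on who has a pregnancy test

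*Combined protocol and SAP*

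**What the plan says.** Two of the exclusions in section 4.2 concern reproduction. Item 4 excludes "Pregnancy or breastfeeding (modafinil is contraindicated in these conditions"). Item 5 excludes women who rely on hormonal contraception "AND concomitant unwillingness to use alternative non-hormonal means of birth control (spermicide or condoms) during the course of the study", and the reason it gives is the drug's effect on oral contraceptives.

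Section 1.3 goes further, but as advice. It recommends that "use of alternative or concomitant methods of contraception while taking modafinil and for one month after discontinuation of modafinil treatment is recommended", in a sentence about hormonal methods. It then says that women of childbearing age will "be advised to use a form of birth control that does not involve hormonal contraception (spermicide or condoms) during the study". The same advice covers the month following the end of modafinil.

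On testing, section 1.3 says that "a urine pregnancy test will be required prior to study enrollment". Section 6.1 lists "Pregnancy test (For individuals of childbearing age who identify their pregnancy status as unsure"). The schedule in section 6.9 shows a urine test at baseline only, where applicable.

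On drug supply, section 5.3 says that "Modafinil will be dispensed for Group 2 and 3 patients following 1 week of baseline actigraphy monitoring and at 8 weeks". Pregnancy is a modafinil stopping rule in section 13. Section 12.2 states that "The informed consent form is considered to be part of the protocol".

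**The concern.** The entry rule screens women who have partial protection against pregnancy and passes over women who have none. Both can be randomized to a drug that item 4 treats as contraindicated in pregnancy. Section 1.3 addresses its advice to all women of childbearing age, so the criterion is narrower than the safety text it should enforce, and no reason is given for the difference.

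The testing text adds to this. A woman who is confident that she is not pregnant is untested under section 6.1, although section 1.3 describes a test as required. At stake is the safety of the participant and of a possible pregnancy. No estimate or test in the analysis plan depends on it.

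**Working it through.** The plan gives no figure on this point, so the check is mainly one of logic.

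**Item 5 by case.** The rule is: exclude if (relies on a hormonal method) AND (unwilling to use a non-hormonal one).

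| Relies on hormonal method | Unwilling to use non-hormonal method | Excluded by item 5? |
|---|---|---|
| yes | yes | yes |
| yes | no | no |
| no | yes | **no** |
| no | no | no |

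The third row contains the woman at issue: she uses nothing and will use nothing.

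**Whether another criterion reaches her.**
- Item 4 covers current pregnancy and breastfeeding; she is neither.
- Item 11 is discretionary and covers medical, neurological or psychiatric conditions. Contraceptive practice is not one of these.
- The five inclusion criteria in section 4.1 do not mention contraception.
- Section 5.1 randomizes those who meet all criteria, so she is eligible as the rule stands.

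**Chance of a modafinil arm.** Groups 2 and 3 of three equal arms (sections 5.1 and 6.3): 1/3 + 1/3 = 2/3.

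**Length of treatment.** 12 weeks (section 6.7) × 7 = 84 days at most.

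**Time since the only scheduled test point.** Day 1 falls 7 to 14 days after the baseline visit (section 6.6).
- Baseline visit to end of treatment: 7 + 84 = 91 to 14 + 84 = 98 days.
- Baseline visit to the nominal week 8 supply: 7 + 56 = 63 to 14 + 56 = 70 days, before the ±14-day window.
- Pregnancy tests scheduled after baseline (section 6.9): 0.

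**The two testing statements side by side.**
- Section 1.3: test required before enrollment.
- Section 6.1: test only for those of childbearing age who say they are unsure.
- Section 6.9: test at baseline where applicable.

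Under sections 6.1 and 6.9 a woman who reports that she is sure has no test. Under section 1.3, read as it stands, she has one. The sections give different instructions for the same visit.

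**Later detection.** The directed adverse-event questions in section 7.5 do not name pregnancy. The follow-up history in section 7.3 concerns conditions relevant to MS, fatigue or modafinil side effects. A pregnancy may come to light at these contacts, but no step is designed to find it.

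**The case against.** The best reply is that the plan handles these women by counselling. Section 1.3 advises all women of childbearing age, a neurologist assesses eligibility (section 6.1), and a study neurologist prescribes the drug (section 5.3). If the baseline visit comes more than two weeks after pre-screening, staff ask about pregnancy again (section 6.6). Pregnancy stops modafinil (section 13). Item 5 also has its own stated purpose: women who may wrongly think that their hormonal method still protects them. In a pragmatic trial of treatments in routine use, excluding that group and counselling the rest is a position a sponsor could defend.

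Much of this stands as mitigation. A reader might infer that the protocol is silent on contraception for women who use no hormonal method; section 1.3 shows that it is not. But advice can be declined without loss of eligibility. No criterion tells the neurologist to exclude a woman who declines it. The stopping rule acts only after conception is recognized.

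Two further objections hold. The consent form counts as part of the protocol and is not in the public copy, so a contraceptive undertaking there cannot be ruled out. And the testing mismatch is a separate point that does not prove the gap in item 5. It could be defended by treating section 1.3 as a summary and section 6.1 as the operating rule, but then section 1.3 promises more than is done.

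**Conclusion.** The gap in the wording of section 4.2 is real. A non-pregnant, non-breastfeeding woman able to conceive who uses no contraception and declines the advice meets the listed criteria, with a 2/3 chance of assignment to up to 84 days of modafinil. The conflict between sections 1.3 and 6.1 on testing is real too, and stands independently.

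Three stronger readings are not supported:
- **That 91 to 98 days is drug exposure.** It is time since the baseline test point and includes 7 to 14 days before Day 1. Exposure is at most 84 days, and less if a pregnancy is recognized and the drug is stopped.
- **That fetal harm has been shown.** The documents describe no specific fetal harm. Section 1.3 rests the pregnancy exclusion on the package insert, which they do not reproduce.
- **That the whole plan lacks a contraception requirement.** The missing consent form prevents that conclusion; only the section 4.2 text is established.

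The number affected is unknown and could be zero. The documents do not give the sex mix, the share able to conceive, or contraceptive use and willingness. Power and the primary analysis are untouched. The point merits a short amendment because the change is small and the testing part only carries out what section 1.3 already states.

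**What to change.** **1. Reword item 5**, for example:

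> For female participants able to become pregnant, including those on hormonal contraception: unwillingness to use non-hormonal birth control (e.g., spermicide or condoms) for the whole study and, if assigned modafinil, for one month after stopping it (modafinil is contraindicated in pregnancy and may make hormonal contraception less effective). Women who are surgically sterile, postmenopausal, abstinent, or whose only partners are female or vasectomized are exempt.

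This keeps the duration that item 5 already sets, names hormonal users so that the present safeguard is not weakened, and matches the one-month advice in section 1.3. For participants followed to week 24 the extra month falls inside the study: 84 + about 30 = 114 days after Day 1, against 168 − 30 = 138 days for the earliest week 24 assessment. It matters mainly for those who leave early.

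**2. Align testing.** Change section 6.1 and the schedule so that every participant able to become pregnant has a urine pregnancy test before randomization. If the consent form lacks a matching undertaking, add one.

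**Cost.** The text changes are one criterion, one line in section 6.1, one schedule entry, one pre-screening question and possibly one consent line. More urine tests are needed, and for virtual visits a kit must arrive before randomization. A few more women are excluded, including some who would have received CBT only. That cannot be avoided if all three arms are to be drawn from the same eligible population, and item 5 already works this way for hormonal users.

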5. STUDY TREATMENTS

5.1 Allocation to Treatment (see also 6.4)

Randomization Process (see also section 6.3): Participants who meet all Inclusion/Exclusion criteria will be randomized (1:1:1 randomization) to CBT (Group 1, n~100), modafinil (Group 2, n~100), or combination CBT+modafinil after the participant has signed consent and completed the baseline activities.

5.2 Blinding

The subject, PI, co-investigators, interventionists, and coordinators will not be blinded.

5.3 Interventions:

Telephone-based CBT: Cognitive Behavioral Therapy for fatigue (CBT – see table 1), also commonly referred to as “fatigue self-management”, was chosen as a comparator given its endorsement in MS fatigue treatment guidelines based on previous efficacy studies demonstrating its benefits in MS. For this study, we will use telephone-delivered CBT for fatigue self-management, which also has a strong evidence-base for its use in MS patients. Developed and tested by one of our study investigators ([name]), this treatment is routinely utilized in her clinical practice to manage several chronic symptoms in MS including pain, depression, and fatigue in MS. In her primary trial of this intervention using the telephone-delivered treatment, which targeted MS-related pain and depression as well as fatigue, 50% of fatigued participants with MS had a clinically meaningful reduction in pain impact that was maintained at 6- and 12-months post treatment. This treatment will be delivered one-on-one via telephone by study interventionists with special training in CBT for symptom management and in telehealth delivery. The team of psychologists includes Drs. [name], [name], [name], and [name], who are all licensed clinical psychologists, who will supervise the two study interventionists (one per study site). Study interventionists will be either licensed clinical psychologists, clinical psychology pre-doctoral students or postdoctoral fellows, or Master’s level social workers. Currently, the primary interventionists are [name], MSW at UM (Drs. [name] and [name] secondary/back-up interventionists) and [name], MSW, [name], and [name], MS at UW (Drs. [name] and [name] secondary/back-up interventionists).

The study interventionists will be trained and supervised in the intervention by the study psychologists, including [name] (author of the telehealth treatment manual, on which this study is based) and [name] at UW, and Drs. [name] and [name] at UM. Training will include readings, didactics, and ongoing review and supervision of recorded sessions. A fidelity protocol will include therapist manuals, protocol checklists, weekly supervision meetings, and an ongoing independent review of randomly selected digital recordings from at least 10% of all sessions. These procedures will ensure therapist fidelity to the CBT treatment (i.e., make certain that patients assigned to CBT get CBT as prescribed in the treatment manual). If poor treatment fidelity is observed, that therapist will receive corrective feedback, additional training, and have all sessions reviewed to ensure 100% adherence to the protocols.

Table 1. Major components of the manualized CBT fatigue self-management intervention
Overall treatment goals: Inform participants about fatigue in MS and engage patients to learn and apply fatigue self-management skills tailored to their strengths and priorities. Key self-management skills include: energy conservation/self-pacing, self-monitoring, sleep behaviors, identifying strengths and priorities, goal-setting (based on individual values), behavioral activation, relaxation techniques, and managing thoughts and emotions.
Session Content (8 weekly sessions and 2 booster sessions; each session 45-60 minutes)
Introduction to MS-related fatigue and fatigue self-management -Factors that contribute to MS fatigue, self-management philosophy, self-monitoring, identifying strengths
Energy management - Self-monitoring check-in, energy management strategies/priorities, energy conservation/pacing training, staying active
Sleep - Sleep behavior assessment, sleep education about sleep regulation, establish a plan for healthy sleep hygiene, problem-solving barriers to sleep disturbance (including morningness/eveningness tendencies); energy management check-in
Goal setting and identifying stressors -Exploring priorities, setting goals, stress response, diaphragmatic breathing (intro to relaxation); energy

management check-in
Working with thoughts (part 1) - Identifying/label thoughts, thought stopping, distraction; relaxation practice; energy management check-in
Working with thoughts (part 2) - Challenging unhelpful thoughts, evidence gathering, alternative thoughts; relaxation practice; energy management check-in
Managing emotions - Emotions and fatigue, living in the present, nurturing positive emotions, gratitude, guided imagery; energy management check-in
Building resilience and moving forward - Designing a personal fatigue self-management plan, skills relapse prevention, building resilience
Two 15-20 minute calls between weeks 8-12, to review and troubleshoot implementation of fatigue self-management skills, including their personal self-management plan.

Modafinil: Modafinil will be prescribed by one of the neurologists on the study team. Modafinil (2-[(diphenylmethyl) sulfinyl]acetamide) is a centrally-acting oral agent that is FDA-approved to improve wakefulness in patients with excessive sleepiness associated with narcolepsy, obstructive sleep apnea, or shift work disorder. The mechanism(s) through which modafinil promotes wakefulness is unknown. Modafinil's benefits for fatigue in MS have been demonstrated in 5 previous studies. Three successful open label studies that used various subjective fatigue measures, demonstrated a benefit of modafinil on fatigue intensity. A single-blind placebo-controlled study also demonstrated a significant improvement in fatigue intensity with modafinil in a recent study. One 8-week double-blind placebo-controlled trial which examined the effects of modafinil on fatigue intensity showed a significant improvement in fatigue with modafinil.

Modafinil will be dispensed for Group 2 and 3 patients following 1 week of baseline actigraphy monitoring and at 8 weeks. At baseline, participants will be prescribed the 100 mg pills (enough to take up to 4 pills per day). They will be advised to take 100 mg once a day (upon awakening) as a starting point for the first week. Depending on results, participants will be allowed to adjust their dose based on the following scenarios:

- If the 100 mg/day dose effectively treats their fatigue throughout the day, participants will remain on this dose.
- If the 100 mg/day dose is adequate, but of insufficient duration, participants will be allowed to take another half pill or full pill around lunchtime (early afternoon: at least 8 hours before bedtime) for a total dose of 150 mg or 200 mg a day.
- If the 100 mg/day dose provides insufficient relief of fatigue, participants may increase the dose to 200 mg/day (upon awakening).
- If the 200 mg/day dose is adequate, but of insufficient duration, participants will be allowed to take another 1 or 2 pills around lunchtime (early afternoon: at least 8 hours before bedtime) for a total dose of 300 mg or 400 mg a day (max dose = 400 mg per day).
- If the 100 mg dose is perceived by the participant to be helpful with fatigue, but associated with excessive side effects (see 1.3), participants will be allowed to decrease their dose to 50 mg, once or twice daily, depending on duration of effect. A pill cutter will be provided by the study team if necessary.

*Participants who report a history of liver problems, participants age 65 or older, participants who use warfarin, phenytoin, MAOIs or cyclosporine†, and participants in whom the investigators think could be at increased risk for side effects, will only be permitted to take ½ of the maximum daily dose, prescribed enough pills to take a maximum of 1 pill twice a day (200 mg/per day) unless they have previously tolerated and required a higher dose prior to enrolling (in which case they will be allowed to return to their previously tolerated dose, up to 400

mg per day) . At baseline, these participants will be prescribed the 100 mg pills. They will be advised to take 50 mg once a day (upon awakening) as a starting point for the first week (A pill cutter will be provided by the study team if necessary.). Depending on results, participants will be allowed to adjust their dose based on the following scenarios:

- If the 50 mg/day dose effectively treats fatigue throughout the day, participants will remain on this dose.
- If the 50 mg/day dose is adequate, but of insufficient duration, participants will be allowed to take another ½ pill around lunchtime (early afternoon: at least 8 hours before bedtime) for a total dose of 50 mg twice a day.
- If the 50 mg/day dose provides insufficient relief of fatigue, participants may increase the dose to 100 mg/day (upon awakening).
- If the 100 mg/day dose is adequate, but wears off more quickly than desired, participants will be allowed to take another half pill or full pill around lunchtime (early afternoon: at least 8 hours before bedtime) for a total dose of 150 mg or 200mg a day (max dose = 200 mg per day).

A medication dispensing log that shows how much drug that was dispensed for each participant at each time point (baseline and week 8) will be used for drug medication review.

†if randomized to a modafinil treatment arm, participants on these medications will be told to inform their prescribing providers of the addition of modafinil to their regimen, to allow the opportunity for additional blood monitoring if the prescriber thinks this is necessary

Combination CBT+modafinil: The CBT+modafinil combination therapy will entail simultaneous engagement in both therapies as described above.

